## Statistical analysis Plan

Sample size justification: If we estimate in relation to the response variable "severity" that 60% of the patients before the intervention present moderate-severe rhinitis and this percentage is expected to be reduced to 30% after 12 months, 51 patients would be needed to detect this difference as statistically significant with 95% certainty, a statistical power of 80% before a bilateral approach of paired data.

All data will be collected in a data base and analysed with SPSS version 20.0 (SPSS Inc. Chicago, Illinois).

Deviation (SD) or interquartile range will be used to describe quantitative variables. For categorical variables, the frequency and percentage will be used. Sample normality will be assessed using the Kolmogorov-Smirnov test. The univariate analysis will be used for comparing measures, either the Student's t-distribution or the Mann Whitney U test depending on the application conditions; for comparing proportions, the chi-squared test or Fisher's exact test will be used. A correlation study will be carried out between quantitative variables using the Fisher or Spearman's statistical test, according to the application conditions. Significance will be set at  $p < 0.05$ .

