## **Material and methods: Patients**

**Study Design:** This will be a prospective quasi experimental non-randomized controlled pre and post-test study. Informed consent (see page 5) will be obtained from all patients in accordance with the Declaration of Helsinki of 1975, revised in 2013. This study has been approved by the Regional Research Ethics Committee of Galicia (Ref: 2015/280). Patients will be recruited in January 2021 and operated in Allergology and Otorhinolaryngology service in CHUAC (A Coruña University Hospital) in January 2021.

**Inclusion criteria:** patients aged 18-65, diagnosed with AR and DS, will be recruited. DS will be determined by rhinoscopy findings. AR diagnosis will be established clinically (history and physical examination) and testing for specific allergen sensitization (positivity > 3 mm). Studied allergen will be pollen, dust mite and fungi. Symptoms of AR should have at least 1 year evolution. AR Classification will be performed according to Aria 2008 (12), as “Intermittent AR” (less than 4 days per week symptoms) and “Permanent AR” (more than 4 days per week symptoms).

Patients with none of these symptoms will be recorded as mild nasal obstruction: sleeping disorders, daily activity impairment, absence with work or school. If the patient had any of those symptoms were classified as moderate-severe nasal obstruction.

**Exclusion criteria:** Patients with less than 1-year AR symptoms, patients treated with specific immunotherapy against allergen, patients undergoing simultaneous surgical procedure (e.g. turbinate reduction), smokers, chronic obstructive pulmonary disease, psychiatric disorders, malignant tumours, severe hepatopathy, obstructive sleep apnoea, previous nasal surgery.

[figure not shown]
**Intervention:** patients will be screened and surgical procedure will be performed by the same surgeon. Variables will be collected from clinical history before and one month after surgery.

After screening, patient's obstruction will be evaluated by anterior rhinomanometry (aRNM) ( $\text{cm}^3/\text{s}$ ) with Rhinospir Pro-165 Sibelmed® (Barcelona, Spain). Classification from mild, moderate, severe or very severe will be determined according to Rhinomanometric grading.

Quality of life (QoF) will be scored through ESPRINT scale. ESPRINT is a validated Spanish questionnaire about daily life activity, sleep, psychology and affection's perception in AR patients (13).

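### The one powered comparison (60% to 30%, paired, 51 patients) is set at 12 months, but data are collected at one month, and no paired test is named for it

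*Combined protocol and SAP*

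**What the plan says.** The Study Design paragraph of Material and methods describes the study so: "This will be a prospective quasi experimental non-randomized controlled pre and post-test study". The Intervention paragraph gives the collection schedule: "Variables will be collected from clinical history before and one month after surgery".

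The Statistical analysis Plan justifies the sample size on a binary severity variable. It assumes that "60% of the patients before the intervention present moderate-severe rhinitis" and continues: "this percentage is expected to be reduced to 30% after 12 months, 51 patients would be needed to detect this difference". The calculation uses 95% certainty and 80% power, and is for a "bilateral approach of paired data".

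The same section then lists the tests. Measures are to be compared by Student's t, with pairing not stated, or by "the Mann Whitney U test depending on the application conditions". The rule for the powered type of outcome begins "for comparing proportions, the chi-squared test", with Fisher's exact test as the alternative. McNemar's test, the paired t-test and the Wilcoxon signed-rank test are not named.

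**The concern.** A power statement applies to one outcome, at one time, analysed by one test. Here two of those three do not carry through.

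- **Time.** The assumed fall to 30% belongs to 12 months, while the described data arrive at one month. If the schedule is followed as written, the powered outcome is never observed at the time for which its effect was assumed. A 12-month assessment that was not scheduled may not be recoverable later.
- **Test.** The sample size treats each patient as their own control. Chi-squared, Fisher's exact and Mann-Whitney U treat the before and after values as coming from different people. Followed literally, the plan analyses its one powered comparison with a test whose standard error ignores the pairing, so the error rate and power are not those of the calculation.

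**Working it through.** **Inputs from the Statistical analysis Plan:** p1 = 0.60 before, p2 = 0.30 after, so d = 0.30; two-sided 0.05 (z = 1.96); power 0.80 (z = 0.8416); N = 51.

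**Assumed, because not stated:** the within-patient correlation r between the before and after values. The discordant proportion is ψ = p1 + p2 − 2·p11, with p11 = p1·p2 + r·√[p1(1−p1)p2(1−p2)].

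**Step 1: reproduce 51.** With independent pairs (r = 0), ψ = 0.6×0.7 + 0.4×0.3 = 0.54.

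- McNemar, uncorrected: n = [1.96·√ψ + 0.8416·√(ψ − d²)]² / d² = [1.96·√0.54 + 0.8416·√0.45]² / 0.09 = 44.7.
- Continuity-corrected: (n/4)·[1 + √(1 + 4/(n·d))]² = (44.7/4)·[1 + √(1 + 4/(44.7×0.30))]² = 51.1.

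The stated 51 is therefore approximately reproduced (51 by nearest rounding, 52 rounded up). Exact McNemar power at N = 51 and ψ = 0.54 is 81%. The calculation appears to be a genuine paired one.

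**Step 2: false positives if pairing is ignored.** Take 60% at both times, N = 51. The true variance of the difference is 2·p(1−p)(1−r)/N, whereas chi-squared uses 2·p(1−p)/N. Its approximate rejection rate is 2·[1 − Φ(1.96/√(1−r))], which is 1.9% at r = 0.3 and 0.6% at r = 0.5. Full enumeration at N = 51 gives:

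| r (assumed) | Chi-squared | McNemar, uncorrected | McNemar, exact |
|---|---|---|---|
| 0 | 5.5% | 5.4% | 3.0% |
| 0.3 | 2.2% | 5.0% | 2.9% |
| 0.5 | 0.7% | 4.4% | 2.5% |

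**Step 3: power at the planned effect** (60% to 30%, N = 51, enumeration):

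| r (assumed) | Chi-squared | McNemar, exact |
|---|---|---|
| 0 | 89% | 81% |
| 0.2 | 91% | 90% |
| 0.3 | 93% | 94% |
| 0.4 | 94% | 97% |

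Both tests stay above 80%. The exact test costs power at low correlation and gains it from about r = 0.3 upwards.

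**Step 4: the time point.** The documents give no one-month proportion, so no power can be computed for that time. The range runs both ways. By the Step 1 formula with r = 0 and 60% before, an assumed 25% afterwards needs 39 patients, and an assumed 35% needs 72. Neither figure is a forecast.

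**The case against.** The list of tests is generic, and the paragraph above it already says the data are paired. Student's t could be the paired form, and chi-squared could be meant loosely enough to cover McNemar. The design is also called controlled, so the independent-samples tests might be meant for comparing groups. Some of this stands: it is fairer to say that no paired test is specified than that every listed test is unpaired. But Fisher's exact and Mann-Whitney U have no such second reading. The available text describes no control group, and the powered comparison is explicitly before against after.

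A second objection is that the harm from the test is small. That stands too. With positive correlation chi-squared produces no excess of false positives, and exact McNemar is itself conservative (2.9% against 2.2% at r = 0.3). At r = 0 and 0.2, chi-squared has the higher power of the two. The case for a paired test is that it matches the design and the sample size calculation, not that it rescues power.

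On time, one figure in Material and methods is not shown and might contain a 12-month visit. If so, it would conflict with the Intervention paragraph, and reconciliation would still be needed.

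**Conclusion.** The point holds as two mismatches within the plan. The time point is the weightier one: the effect is assumed at 12 months, and the available text describes collection only before and one month after surgery. The test is the lesser one: the plan names no paired test for proportions or ranks, although its one powered comparison is paired.

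A reader might infer three stronger things that the documents do not support:

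- *That 51 is miscalculated.* It is not; a standard paired formula gives 51.1.
- *That the listed tests inflate false positives or take power below 80%.* For zero or positive correlation they do neither at the planned effect. The type I error of chi-squared is about 2.2% at r = 0.3 and 0.7% at r = 0.5, and at r = 0 there is no distortion from pairing.
- *That a one-month assessment leaves the study underpowered.* No one-month rate is given, so power there is unknown in either direction.

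The textual mismatches are certain. The sizes rest on assumed correlations.

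**What to change.** 1. **Time.** Reconcile the 12 months in the sample size paragraph with the one month in the Intervention paragraph, and state the same time in both. Either the powered outcome is collected when 60% to 30% is assumed, or the assumption is restated and justified for the time actually collected. Keeping 12 months requires a 12-month collection to be written into Material and methods. Keeping one month requires a rationale for the rate at one month and a recalculated N if that rate differs from 30%.
2. **Tests.** In the Statistical analysis Plan, test the before/after binary outcome by McNemar and say in advance which version. The exact and continuity-corrected versions are consistent with 51 patients, each giving 81% power for independent pairs. Use the paired t-test or Wilcoxon signed-rank test for before/after measures. Keep chi-squared, Fisher's exact, the unpaired t-test and Mann-Whitney U for comparisons between different patients. This is SAP wording only and leaves N at 51 if the 60% to 30% assumption stands.

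### The study is designed and sized for paired data, but no valid paired test is named for pre/post proportions or non-normal measures

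*Combined protocol and SAP*

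**What the plan says.** Under Study Design the trial is a "prospective quasi experimental non-randomized controlled pre and post-test study". No comparison group or between-group contrast is described. Under Intervention, "Variables will be collected from clinical history before and one month after surgery", so each patient supplies both values.

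The sample size paragraph of the Statistical analysis Plan assumes that "60% of the patients before the intervention present moderate-severe rhinitis", that "this percentage is expected to be reduced to 30% after 12 months", and that "51 patients would be needed to detect this difference as statistically significant with 95% certainty", with "a statistical power of 80% before a bilateral approach of paired data". (The one-month and 12-month time points must be reconciled, but that is a separate matter; the data are paired either way.)

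The analysis paragraph of the same section says "The univariate analysis will be used for comparing measures", by Student's t or "the Mann Whitney U test depending on the application conditions; for comparing proportions, the chi-squared test" or Fisher's exact. McNemar's test, the Wilcoxon signed-rank test and a paired t-test are not mentioned. No test is assigned to a particular comparison.

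**The concern.** Chi-squared, Fisher's exact and Mann-Whitney U all treat the two sets of values as coming from different patients. Used before versus after surgery, they count 51 patients as 102 independent observations and ignore the correlation between a patient's two values. Only Student's t has a paired form, and the plan does not say which form is meant.

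Choosing among the tests named for proportions and for non-normal measures therefore cannot give a valid pre/post test. With positive correlation the named tests are conservative, so smaller real changes in severity, VAS, ESPRINT, airflow or medication use can be missed. With negative correlation they reject too often. The sample size also rests on a different class of test from the one named for the analysis.

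**Working it through.** **1. The plan's own figure.** Inputs from the sample size paragraph: 60% before, 30% after, two-sided 5%, 80% power, paired. The discordance is not stated; assume the two visits are independent. Then 0.60 × 0.70 = 0.42 of patients improve, 0.40 × 0.30 = 0.12 worsen, psi = 0.54 and d = 0.30.

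- McNemar, normal approximation: n = [1.96√psi + 0.84√(psi − d²)]² / d² = [1.96√0.54 + 0.84√0.45]² / 0.09 = 44.7.
- With continuity correction: (n/4)[1 + √(1 + 4/(nd))]² = 51.1.
- Exact McNemar reaches 80% power at 50 patients.
- For comparison, two independent groups need 42 per group, or 49 with continuity correction.

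So 51 is a McNemar-type figure.

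**2. True error rate of the named test.** With proportion p at both visits, the two-sample test takes the variance of the difference as 2p(1 − p)/n. The actual variance is 2p(1 − p)(1 − phi)/n. The true two-sided alpha is therefore about 2[1 − Φ(1.96/√(1 − phi))], which gives 1.9% at phi = 0.3, 0.6% at 0.5 and 8.6% at -0.3. Full enumeration of all paired 2×2 tables (n = 51, p = 60%, no continuity correction) gives:

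| phi | Two-sample chi-squared | McNemar, asymptotic |
|---|---|---|
| -0.3 | 9.2% | 5.1% |
| 0 | 5.5% | 5.4% |
| 0.3 | 2.2% | 5.0% |
| 0.5 | 0.7% | 4.4% |

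For p anywhere from 30% to 60%, chi-squared alpha is 2.0–2.4% (phi = 0.3), 0.6–0.8% (0.5) and 8.6–9.9% (-0.3). Fisher's exact is lower still at p = 60%: 1.1% at phi = 0.3 and 0.3% at 0.5. Exact McNemar is also conservative (2.9% and 2.5%), but it does not drift towards zero in this way.

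**3. Power for severity, n = 51.** The 60% to 45% effect is an assumption, chosen as half the planned drop.

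| Effect | phi | Chi-squared | McNemar, asymptotic | McNemar, exact |
|---|---|---|---|---|
| 60% to 30% | 0 | 89% | 87% | 81% |
| 60% to 30% | 0.3 | 93% | 96% | 94% |
| 60% to 30% | 0.5 | 96% | 99.8% | 99.6% |
| 60% to 45% | 0.3 | 33% | 44% | 35% |
| 60% to 45% | 0.5 | 30% | 56% | 46% |

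**4. Quantitative outcomes.** Assume 51 bivariate-normal pairs with a mean change of 0.40 SD of the differences, which gives the paired t-test 80% power. Simulation (20,000 trials) gives Mann-Whitney power of about 66%, 50% and 23% at r = 0.3, 0.5 and 0.7, against 78% for Wilcoxon signed-rank. With no change, Mann-Whitney alpha is about 2.1% at r = 0.3 and 0.6% at r = 0.5. If Student's t were run unpaired, power is about 1 − Φ(1.96/√(1 − r) − 2.80), which is 68%, 51% and 22%. Direct simulation puts the last figure nearer 24%.

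**5. If chi-squared were run on the pre-by-post cross-table.** This tests association between visits, not change. With 60% at both visits and phi = 0.3 it is significant 58% of the time although nothing has changed. With the full 60% to 30% drop and phi = 0 it is significant only 5% of the time.

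**The case against.** The strongest reply is that this is a gap and not an error. The analysis paragraph never says that Mann-Whitney or chi-squared will be applied before versus after, the sample size paragraph acknowledges pairing, and Student's t may be the paired form. The named tests would suit comparisons between different patients, such as intermittent against permanent rhinitis, or a control group if *controlled* implies one. The published text is also incomplete in places. None of this supplies a test for the pre/post change in a proportion or a non-normal measure: the sentence naming the tests reads as complete, and no paired alternative is in it.

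Several points on size do stand.

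- Under zero or positive correlation, the likelier case for repeated severity in one patient, alpha is about 5% or less, so a significant result would not be an artefact of the test. Nothing in the documents suggests negative correlation.
- At the planned effect chi-squared exceeds 80% power in every row of the table, and at phi = 0 it beats exact McNemar.
- For 60% to 45% at phi = 0.3 the gap to exact McNemar is only 33% against 35%.
- The larger losses need stronger correlation and concern outcomes for which the plan states no power. They were simulated on normal data, whereas the plan would use Mann-Whitney on non-normal data.
- The cross-table figures describe a possible misuse that the plan does not propose, and carry little weight.

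**Conclusion.** The concern holds. The design and sample size are paired, while every test named for proportions and for non-normal measures is for independent samples, and the form of Student's t is left open. Applied to the pre/post comparison, the stated rule gives error rates that are not the nominal 5%: 2.2% to 0.7% for chi-squared at phi = 0.3 to 0.5, and about 9% at phi = -0.3. The main cost is p-values that do not mean what they say, and reduced sensitivity to modest changes and on the continuous outcomes. It is not a failure to detect the planned 60% to 30% drop.

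The direction follows from the variance formula. The exact sizes rest on the assumed correlations, the assumed smaller effects and, for continuous outcomes, normal data. The number 51 itself is sound for a paired test if the visits are independent or positively correlated.

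**What to change.** In the Statistical analysis Plan, assign a test to each comparison:

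- **Pre/post severity and other two-class outcomes:** McNemar's test, stating in advance whether exact or asymptotic.
- **Pre/post rhinomanometry, ESPRINT and VAS:** paired t-test, or Wilcoxon signed-rank where the differences are not normal or the outcome is an ordinal grade.
- **Normality:** assessed on the within-patient differences.
- **Unpaired t, Mann-Whitney, chi-squared and Fisher's exact:** kept only for comparisons between different patients, with those comparisons named.
- **Sample size:** state the discordance or correlation behind 51.

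This changes wording only. The tests are standard and no new data are needed. At phi = 0, 51 patients give 81% power by exact McNemar or 87% by the asymptotic test, and more with positive correlation. If phi were -0.3, power at the planned effect would be 70% exact or 77% asymptotic, which is why the assumption should be written down.

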Symptoms like sneezing, itchy nose, ocular symptoms and nasal obstruction will be evaluated with visual analogue scale (VAS) and clinical history. VAS score will be classified as mild (1-3), moderate (4-6) and severe (7-10).

Medication (intranasal corticosteroid, ant leukotrienes, antihistamine eye drops, antihistamine) and its frequency (less than 2 intakes per week or more than 2 intakes per week) will also be registered.

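### The study is sized on severity, but the SAP does not make severity decide the conclusion: every comparison is judged at an unadjusted 0.05

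*Combined protocol and SAP*

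**What the plan says.** The sample size paragraph of the Statistical analysis Plan begins "Sample size justification: If we estimate in relation to the response variable" severity. It assumes that "60% of the patients before the intervention present moderate-severe rhinitis", falling to 30% at 12 months, and arrives at 51 patients with "a statistical power of 80"%. The words "before a bilateral approach of paired data" make the calculation two-sided and paired.

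The analysis paragraph that follows does not mention severity again. It lists Student's t or Mann-Whitney U for measures, chi-squared or Fisher's exact for proportions, and a correlation study. It closes with "Significance will be set at" p < 0.05. It labels no outcome primary or secondary, gives no testing order and states no adjustment.

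The outcomes are described under Material and methods. Besides anterior rhinomanometry and the ESPRINT questionnaire, the text says "Symptoms like sneezing, itchy nose, ocular symptoms and nasal obstruction will be evaluated with visual analogue scale (VAS) and clinical history". It also says "Medication (intranasal corticosteroid, ant leukotrienes, antihistamine eye drops, antihistamine) and its frequency" will be recorded.

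**The concern.** Sizing a study on one outcome does not by itself make that outcome decide the result. Under the plan as written, a small p-value for nasal itch, or for one drug class, has the same standing as one for severity. A report could claim a significant change after septorhinoplasty on the strength of that one result, even if severity, the only outcome with a power calculation, had not moved. The 5% threshold then describes each test taken alone. It does not describe the error rate of the study's conclusion.

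**Working it through.** **1. The plan's own figure.** The documents give no discordance rate, so I assume that before and after status are independent within patient.
- Improve: 0.60 × 0.70 = 0.42. Worsen: 0.40 × 0.30 = 0.12. Discordant: 0.54. Difference: 0.42 − 0.12 = 0.30.
- Uncorrected McNemar: n = [1.96√0.54 + 0.842√(0.54 − 0.09)]² / 0.09 = 44.7, so 45.
- With continuity correction: (n/4)[1 + √(1 + 4/(0.30n))]² = 51.1, so 52.
- The exact McNemar test first reaches 80% power at n = 50 and has 81.2% at n = 51.

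The stated 51 is therefore consistent with one paired test of severity at two-sided 0.05. It makes no allowance for further tests.

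**2. Counting outcomes.** The plan gives no list of hypotheses, so this count is mine: severity (1), airflow (1), ESPRINT (1), named VAS symptoms (4), drug classes (4); total 11. The drug classes are only said to be recorded, and without them the count is 7. Counting drug frequency, airflow grade, ESPRINT domains or the correlations would raise it.

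**3. Chance of at least one false change.** Assume every null is true and each test has exactly 5% error.
- Independent outcomes: 1 − 0.95^k.
  - k = 7: 30.2%
  - k = 11: 43.1%
  - k = 15: 53.7%
- Equal pairwise correlation ρ, normal approximation: 1 − ∫[Φ((1.96 − √ρ·g)/√(1−ρ)) − Φ((−1.96 − √ρ·g)/√(1−ρ))]^k φ(g) dg, integrated numerically.

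| ρ (assumed) | 11 outcomes | 7 outcomes |
|---|---|---|
| 0 | 43.1% | 30.2% |
| 0.3 | 37.5% | 27.2% |
| 0.5 | 30.4% | 23.0% |
| 0.7 | 22.3% | 17.8% |
| 0.9 | 13.1% | 11.4% |

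**4. If the named unpaired tests are used.** Mann-Whitney, chi-squared and Fisher's exact treat before and after as separate groups. With within-patient correlation r, the per-test error is approximately 2[1 − Φ(1.96/√(1−r))].
- r = 0.3: 1.9% per test. For 11 independent outcomes, 1 − (1 − 0.01915)^11 = 19%.
- r = 0.5: 0.6% per test. For 11 independent outcomes, 1 − (1 − 0.00557)^11 = 6%.

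**5. Two remedies compared.** With severity as the single primary outcome, the error of the main conclusion is 5% and N stays at 51. If all 11 were kept co-equal under Bonferroni, the per-test level would be 0.05/11 = 0.0045. N for severity would rise from 45 to 79 (uncorrected) or from 52 to 85 (continuity-corrected). Power at 51 would fall from 85% to 53% (uncorrected formula).

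**The case against.** - **Severity is already the lead outcome.** A reader might infer that the study has no primary outcome at all. The documents do not support that. Severity is singled out for the sample size, and the sentence in the Introduction that states the main objective is cut off in the supplied text, so its content is unknown and I do not rely on it. What stands is narrower: the analysis text gives severity no deciding role and gives the other outcomes no lesser one.
- **The count and the correlations are not in the plan.** This is correct. Independence is also unlikely: the Methods define moderate-severe status partly by sleep and daily activity, which ESPRINT also covers, and rhinomanometry and the obstruction VAS both address obstruction. This pulls the figure down from 43%. Nor is 43% a ceiling, since more outcomes would raise it.
- **The named tests would run below 5%.** This is also correct, and it could take the rate to about 19% or 6%. But that protection would come only from tests that ignore the pairing on which the sample size rests. It disappears once the tests match the design.
- **The percentages might be read as the chance of a false effect of surgery.** They are not. They cover false change only. A real change without a surgical cause, such as regression to the mean, lies outside them, and naming a primary outcome does not address it.

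**Conclusion.** The point holds in this form: severity sizes the study but is not declared primary for inference, and an unadjusted 0.05 applies to everything, so any one outcome can carry the conclusion.

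The size is illustrative. If all nulls are true and valid paired tests are used, the chance of at least one false change is 13% to 43% for 11 outcomes, as the assumed correlation falls from 0.9 to 0. For 7 outcomes it is 18% at correlation 0.7 and 30% under independence. All of these are more than twice the nominal 5%, but none is a property that the documents establish. Unpaired tests would give less, and a longer outcome list would give more. The case for changing the plan does not depend on any one of these figures, because the missing decision rule can be seen in the text.

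**What to change.** In the SAP:

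1. Declare the proportion moderate-severe, the variable behind N = 51, the single primary outcome. Test it with McNemar at two-sided 0.05, and base the main conclusion on that test alone.
2. State which grading is meant. The sample size paragraph refers to moderate-severe rhinitis, while the Methods define moderate-severe nasal obstruction. Reconcile the time point as well: 12 months in the sample size paragraph, one month after surgery in the Methods.
3. Label all other outcomes secondary and report each as a paired change with a 95% CI. Either treat them as exploratory or claim significance only after Holm adjustment. Both options resolve the problem.

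The cost is SAP wording, and N does not change. Some secondary p-values below 0.05 could no longer be claimed as significant. Under Holm with 10 secondary outcomes, the thresholds rise stepwise from 0.05/10 = 0.005 to 0.05, so not every p-value between 0.005 and 0.05 is lost.
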